# 4.9 Criteria for the termination of the trial. Description of the discontinuation criteria for individual participants, parts of the trial and entire trial.

Study participation is voluntary, and participants may withdraw at any time. The DSMB will report to the ethics committees and investigators if stopping the trial is required.

In general, once a participant is randomised, he/she will remain in the study unless the investigator believes it is not safe for the participant to continue. However, the criteria below will be used to determine whether use of the AHCL should be discontinued for a participant.

- 1. Severe hypoglycaemia (seizure or coma or any episodes requiring third party assistance).
- 2. Severe diabetic ketoacidosis (venous ph <7.2)
- 3. Participant pregnancy
- 4. Non-compliance with the protocol or development of a new medical condition or need for chronic use of a medication which in the judgment of the investigator increases risk for the participant

If AHCL use is stopped according to the above criteria, but the participant is willing, they will remain in the trial and will continue to make all of the scheduled visits and participate in all monitoring. The primary analysis will be intention to treat. Since participants in the usual care arm are following their normal diabetes care regimen, there will be no change in their participation in the trial if they experience one of the events that would trigger stopping.

Criteria for Suspending/Stopping Overall Study

The DSMB will have the responsibility of determining if the overall study should be stopped. In case of a recurring system malfunction or participant safety issue observed with multiple participants, the overall study will be suspended while the problem is diagnosed. The study may resume if the underlying problem can be corrected by a protocol or system modification that will not invalidate the results obtained prior to suspension.

An instance of severe DKA from Automode use (algorithm-related) in the AHCL group will result in temporarily stopping additional enrolment of participants until DSMB review of the data to determine whether the event was triggered by the system or not and whether it is safe to proceed. The currentlyenrolled participants will continue use of the system during this time unless the DSMB determines it is unsafe for them to do so. The overall study will be stopped if the number of participants developing severe DKA in the AHCL group exceeds the number in the control Group by 5 or more at any time. However, the DSMB will have the authority to stop the study at any time because of safety concerns even if this criterion is not met.

The Coordinating Center will track all participant withdrawals. If the above rule is met (AHCL Group exceeding control Group by 5 or more), an emergency meeting of the DSMB will be convened within 7 days to review the data. In addition, the DSMB Chair may request a meeting at any time.

4.10 The identification of any data to be recorded directly on the Case Report Forms (CRFs) (i.e. no prior written or electronic record of data), and to be considered to be source data.

Every participant will be given a unique study number. All data on CRF will be de-identified.

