The system in Manual Mode can be programmed to automatically suspend basal insulin delivery for up to two hours when the sensor glucose falls below a predefined or predicted threshold value. In Auto Mode, the system can be programmed to automatically calculate the insulin dose based on information received from continuous glucose monitoring (CGM).

The AHCL has the following enhancements from the commercial Medtronic 670G pump with HCL:

- Additional setpoint option of 5.6 mmol/L (in addition to 6.7 mmol/L and temp target of 8.3 mmol/L). Correction target is 6.7 mmol/L for both 5.6 mmol/L and 6.7 mmol/L setpoints.
- Automatic correction bolus delivery when the pump has been delivering at the maximum allowable basal rate and sensor glucose remains elevated above the correction target when pump is in Auto Mode
- Ability to make therapy adjustment based on sensor glucose values without the requirement for a confirmatory self-monitoring blood glucose (SMBG) measurement
- Other updates to the Auto Mode algorithm intended to reduce the frequency of exits from Auto mode and further minimize glucose excursions.

The MiniMed™ 670G Version 4.0 (AHCL) insulin pump uses the same hardware as the MiniMed™ 670G pump with the advanced algorithm. In view of the recall on insulin pumps with clear retainer rings, the study will use the 780G insulin pump with the same algorithm, which has the added feature of bluetooth wireless communication with the compatible devices in the MiniMed™ 780G System connectivity.

The MiniMed™ 780G Pump works with the following major components: 1) Continuous Glucose Monitoring (CGM) that includes the Guardian Link (3) Transmitter that is connected to the Guardian Sensor (3) to receive sensor glucose values at 5 minute intervals; 2) blood glucose meter (Roche Accu-Chek®) that will be used to calibrate the sensor and has the ability to send blood glucose values

wirelessly as a convenience to the user; 3) MiniMed™ Clinical App to allow upload of data wirelessly, for sharing of glucose levels

To maintain the same functionality as the 670G 4.0 pump for the trial, we will not be using the Minimed™ Clinical App.

**Glucose monitoring:** All participants will be issued with the CONTOUR® NEXT LINK 2.4 from Bayer. This glucose monitor requires CONTOUR PLUS test strips.

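### Section 4.9 requires an enrolment pause and a DSMB attribution review after one algorithm-related severe DKA, but not after a first algorithm-related hypoglycaemic seizure or coma

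*Protocol*

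**What the plan says.** Section 4.9 has two layers. The first concerns the individual. Four criteria guide whether AHCL should be discontinued, and the first two are "Severe hypoglycaemia (seizure or coma or any episodes requiring third party assistance") and severe DKA. A participant taken off AHCL is not lost: if AHCL is stopped "but the participant is willing, they will remain in the trial".

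The second layer concerns the whole study, and there the two events part.

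- **Single-event trigger, severe DKA only:** "An instance of severe DKA from Automode use (algorithm-related) in the AHCL group will result in temporarily stopping additional enrolment". The pause lasts until the DSMB has reviewed the data "to determine whether the event was triggered by the system or not and whether it is safe to proceed". Participants already enrolled go on using the system in the meantime unless the DSMB finds that unsafe.
- **Between-arm rule, severe DKA only:** the study stops if the "number of participants developing severe DKA in the AHCL group exceeds the number in the control Group by 5 or more".
- **General suspension clause, any event type:** it applies to a system malfunction that recurs or to a "participant safety issue observed with multiple participants, the overall study will be suspended while the problem is diagnosed".
- **Discretion:** the DSMB may stop the study at any time on safety grounds, and its Chair may ask for a meeting at any time.

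Outside 4.9, section 8.4 lists severe DKA and severe hypoglycaemia as the first two severe adverse events. Section 2.2 gives as an enhancement over the commercial pump "Automatic correction bolus delivery when the pump has been delivering at the maximum allowable basal rate" and sensor glucose stays above the correction target.

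**The concern.** The protocol gives severe DKA and severe hypoglycaemia equal rank wherever it defines or lists them, then gives only one of them a mandatory first-event response. It offers no reason for the difference.

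The protocol's own account of device risk makes the omission harder to explain. The heading on auto correction in section 8.1 names both hypo- and hyperglycaemia. The only mechanism described under it is a sensor that reads well above blood glucose, so that too much insulin is given and glucose falls too low. The paracetamol warning in the same section points the same way: the drug falsely raises sensor readings, and users are told to switch auto correction off.

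At stake is whether someone independent must decide, after a first seizure or coma that looks algorithm-related, if the device caused it before more young people are randomised to the device. For severe DKA that decision is compulsory. For hypoglycaemia it depends on the DSMB choosing to take it up.

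**Working it through.** The point is textual and no arithmetic applies. The check sets out what the protocol provides after a first algorithm-related event of each kind in one AHCL participant.

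| Provision | Severe DKA | Severe hypoglycaemia with seizure or coma |
|---|---|---|
| Criterion for stopping AHCL in that participant (4.9) | Yes | Yes |
| Listed severe adverse event (8.4) | Yes | Yes |
| Reported within 24 hours (8.2) | Yes | Yes |
| DSMB sees the data (8.3, 10.2) | Yes | Yes |
| DSMB may stop the study; Chair may call a meeting (4.9) | Discretionary | Discretionary |
| General suspension clause (4.9) | Not met by one first event | Not met by one first event |
| Enrolment pause after one event (4.9) | **Mandatory** | **None** |
| DSMB attribution decision after one event (4.9) | **Mandatory** | **None** |

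Three steps follow.

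1. *Does the general suspension clause fill the gap?* It needs either a recurring malfunction or a safety issue seen in more than one participant. A first event in one person is neither. The clause does cover hypoglycaemia once the problem recurs or spreads, so the gap is confined to the first event.
2. *Do the 24-hour reports fill it?* Section 8.2 sends hospital admissions for severe hypoglycaemia to the principal investigator. It sends serious adverse events to the investigators, lead site, sponsor and regulator, and severe ones also to the manufacturer. The DSMB is not a named recipient, and no pause or attribution decision is attached to a report.
3. *Does DSMB discretion fill it?* The DSMB can act, but need not. The same discretion exists for severe DKA, and a mandatory step was still written for that event.

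The two columns therefore agree on every first-event provision except the last two rows.

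**The case against.** The strongest reply is that this is a design choice that suits the population. Participants have HbA1c above 8.5%, and sections 6.3 and 8.2 describe their adherence as suboptimal. Recent severe DKA is an exclusion criterion in 5.3, whereas recent severe hypoglycaemia is not. Section 8.1 treats both low and high glucose as background risks of insulin that the device is meant to reduce. Cover for hypoglycaemia is also real: individual discontinuation, rapid reporting, monthly monitoring by the coordinating investigator, DSMB data access, and a suspension clause that is not limited to DKA.

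Much of this stands. Nothing in 4.9 is contradictory, and the reasons for a DKA trigger are sound. But they explain why DKA is in the sentence, not why hypoglycaemia is left out, given the hazard described under auto correction. The existing cover narrows the gap without making any first-event review compulsory.

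Two stronger inferences are tempting and are not supported. The first is that a hypoglycaemic seizure would go unreviewed; the DSMB has the data and the authority to act. The second starts from the sentence "The Coordinating Center will track all participant withdrawals" and infers that nobody counts the severe DKA cases that the between-arm rule compares. That sentence does not say that only withdrawals are tracked, and severe DKA already reaches the lead site and sponsor within 24 hours as a severe adverse event.

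**Conclusion.** The point holds as a limited gap in the safety rules. After a first algorithm-related hypoglycaemic seizure or coma, 4.9 requires neither an enrolment pause nor a DSMB decision on causation, although it requires both after the equivalent severe DKA. The change is worth making because it is small and bears on participant safety. It does not affect the efficacy analysis.

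No number is attached. A reader might want the chance of such an event, or the number of participants randomised to AHCL before the DSMB acts. The protocol gives neither a severe-hypoglycaemia rate nor a DSMB response time for this situation. Exposure also extends beyond the primary phase, since controls are offered AHCL in the extension. Any figure would come from assumptions alone.

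The conclusion rests on reading the general suspension clause as not triggered by one first event in one participant, which is its plain meaning. It does not imply that a between-arm stopping count for hypoglycaemia is needed.

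**What to change.** In the single-event sentence of 4.9, widen the trigger to read: *An instance of severe DKA, or of severe hypoglycaemia with seizure or coma, from Automode use (algorithm-related)*. Leave the rest of the rule unchanged. Limiting the trigger to seizure or coma, rather than every episode needing third-party help, keeps the pause for the gravest events.

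The general suspension clause needs no edit, because severe hypoglycaemia is already a participant safety issue within its meaning.

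The cost is one wording change, with no new data collection since these events are already reported. In practice it means an occasional extra DSMB referral and a short halt in enrolment. The pause itself protects new enrolees only: current participants continue unless the DSMB decides otherwise, and once recruitment has closed only the attribution review has any effect.

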#### 5. Source and Selection of Participants

5.1 **Source of participants** - research population, sample size, source, and sampling frame (if possible, split by site if multicentre trial).

Eligible participants will be identified through the Western Australian Children's Diabetes Database (WACDD) and state specific databases. A generic invite with the information sheet will be sent electronically. Participants will also be identified during their clinic visits. We may also use advertisements, notices, and/or media to recruit participants. Examples include flyers posted in public settings, newspaper ads, and radio and television advertisement. All advertisements and recruitment materials (e.g., video, audio, and telephone scripts) will be submitted to HREC for prior approval. Indirect recruitment will also be conducted in these sites with authorised access request: Fiona Stanley Hospital, Sir Charles Gairdner Hospital, and Rockingham General Hospital.

- 5.2 **Participant inclusion criteria.** Describe appropriate criteria for special risk populations (e.g. women of reproductive age, participants with disease states or organ impairment).
  - 1. Type 1 diabetes (diagnosis consistent with American Diabetes Association Classification of Diabetes Mellitus, diagnosed at least 1 year ago)
  - 2. Fasting C peptide <0.1nmol/L (in the absence of hypoglycaemia)
  - 3. Pump therapy for at least 6 months
  - 4. Age 12 to 25 years
  - 5. Recent HbA1c > 8.5% in the last 3 months
  - 6. Mean HbA1c > 8.5% for 6 months
  - 7. Willing to follow study instructions
  - 8. Willing to perform  $\geq$  3 finger stick blood glucose measurements daily
  - 9. Willing to perform required sensor calibrations
  - 10. Capable of reading and understand instructions in English
  - 11. Living in an area with internet and cellular phone coverage
  - 12. Minimum daily insulin requirement (Total Daily Dose) of greater than or equal to 8 units
- 5.3 **Participant exclusion criteria.** May include conditions that increase the risk to the participant, that interfere with the participant's ability to give informed consent or interfere with a participant's ability to comply.
  - 1. Participants using closed loop therapy within the past 3 months
  - 2. Severe DKA in the 6 months prior to the screening visit
  - 3. Use of any non-insulin glucose-lowering agent within the past 3 months

- 4. Commenced CGM in the 3 months prior to the screening visit
- 5. Pregnancy or planned pregnancy within the study period
- 6. Uncontrolled coeliac disease (not following a gluten free diet), or other untreated malabsorption
- 7. Uncontrolled thyroid disease
- 8. Clinically-significant gastroparesis
- 9. Poor visual acuity precluding use of the investigational technology
- 10. Inability or unwillingness to meet protocol requirements
- 11. Severe or unstable medical or psychological condition which, in the opinion of the treating physician and/or investigator, would compromise the ability to meet protocol requirements

# 5.4 **Participant withdrawal criteria** (i.e. terminating investigational product/trial treatment) and procedures specifying:

(a) when and how to withdraw participants from the investigational product/trial treatment; The participant may withdraw from the study at any time. They can do so by contacting the research staff.

(b) the type and timing of the data to be collected for withdrawn participant(s); As this is an ITT, the data for withdrawn participants will be used for analysis

(c) whether and how participants are to be replaced; Participants will not be replaced.

(d) the follow-up for participants withdrawn from the investigational product/trial treatment. The participants will go back on their standard therapy and will be followed up as their regular clinic visits.

#### 6. Treatment of Participants

6.1 **Description and justification for the treatments**, interventions or methods to be utilised (including product name(s), dose(s), dosing schedule(s), route/mode(s) of administration and treatment period(s)) and the follow-up period(s) for participants for each investigational product/trial treatment group/arm of the trial.

The Medtronic advanced hybrid closed loop system compromises the Medtronic MiniMed  $^{\text{TM}}$  670G 4.0 /780G insulin pump containing the closed loop algorithm, a 4th generation glucose sensor and a glucose sensor transmitter. This system is the intervention provided to the participants for 6 months.

Short-acting Insulin is administered subcutaneously via the pump. The pump delivers insulin (microbolus) every 5 minutes (basal insulin) and the amount is dependent on the sensor glucose levels. The system needs the entry of CHO amount by the user at meal times. This HCL system has an advanced closed loop algorithm from the current version being used in two of our research studies (2016087EP and 2016051EP).

# 6.2 The **medications/treatments permitted** (including rescue medication) and not permitted before and/or during the trial.

For severe hypoglycaemia, intramuscular glucagon can be administered.

For ketosis > 0.6 mmol/l with blood glucose > 15mmol/l, insulin (short-acting) is administered with a pen.

This is taught to every family at the time of diagnosis of T1D and review of their knowledge is established in subsequent clinic follow-ups.

#### 6.3 The procedures for monitoring participant compliance.

The study is targeted at patients with poor glycaemic control where adherence to current treatment is suboptimal. Participants randomised to the intervention arm will receive support from the research staff to help them familiarise themselves with the "intervention".

They will also receive assistance to help troubleshoot sensor issues. Participant's pump will be uploaded at each visit and the clinical review at every 3 months will provide an opportunity to engage and encourage the use of the system.

#### 7. Assessment of Efficacy

- 7.1 Specification of the efficacy parameters. Glycaemic control will be measured by HbA1c every 3 months
- 7.2 The methods and timing for assessing, recording, and analysing efficacy parameters. DCA Vantage HbA1c analyser for measuring HbA1c

#### 8. Assessment of Safety

8.1 Summary of known and potential risks and benefits, if any, to research participants.

There is a small risk of insulin pump site and glucose insertion site bruising, or skin reaction. However all participants have used insulin pumps and sensors previously. Any patient receiving insulin at any time has the potential to develop hyper or hypoglycaemia. These devices specifically aim to minimise that potential for that risk.

#### Risks associated with AHCL system in Auto and Manual Mode:

Sensor glucose is populated in the Bolus Wizard automatically by the system when taking a bolus. Sensor glucose is not the same as blood glucose. Sensor performance may occasionally vary from sensor to sensor and in different situations for a sensor, such as on the first day of use.

- Hypoglycaemia or Hyperglycaemia when using sensor glucose values to calculate a meal bolus:
  - If a sensor value is much lower than a blood glucose would be at that time, there is a risk of hyperglycaemia, because the amount of insulin delivered could be smaller
  - If a sensor glucose is much higher than a blood glucose at that time, there is a risk of hypoglycaemia, because the amount of insulin delivered could be larger
  - If participant feels low (but sensor glucose value is not low) or if participant is experiencing severe hypoglycaemia, severe hyperglycaemia or DKA, participant should do a BG check with the meter.
- Hypoglycaemia or Hyperglycaemia when auto correction (auto bolus) is activated:
  - If a sensor glucose is much higher than a blood glucose at that time, there is a risk of hypoglycemia, because the amount of insulin delivered could be larger
  - If participant feels low (but sensor glucose value is not low) and if participant is experiencing severe hypoglycaemia, severe hyperglycaemia or DKA, participant should do a BG check with the meter.

#### Risks associated with Paracetamol use:

• False elevation of sensor glucose readings. The level of inaccuracy depends on the amount of paracetamol active in the patient's body and may be different for each person.

Note: If participant is using paracetamol or medications containing paracetamol (e.g. cold, pain, fever, and cough medications) while in Auto Mode:

- Participant will be instructed by the study doctor not to use sensor glucose readings to make treatment decisions until participant has stopped using products that contain paracetamol
- Participant should take additional blood glucose meter readings to verify glucose levels.
- Participant should turn off Auto Correction.
- Participant should consider exiting Auto Mode.
- 8.2 The **safety parameters** and the methods and timing for assessing, recording, and analysing safety parameters. Include a description of emergency procedures if applicable.

This is a cohort of participants with poor glycaemic control and sub-optimal adherence to treatment and safety measures will be put in place.

- a. Participants will be contacted on a weekly basis (or more frequently as required) for at least 4 weeks after commencement of AHCL to review progress.
- b. Participants with high blood/sensor glucose levels will be advised to test for blood ketones.

Participants in the control group will be advised to follow the clinical pathway while participants in the intervention group will be advised to contact the research doctor/diabetes educator.

- c. . In the event of device (pump) failure, the participant will be advised to switch to their standard pump therapy and contact the research doctor/diabetes educator.
- d. Participants in the intervention group will be informed to contact the research diabetes educator if they experience technical issues with the sensor and/or system
- e. Patients are educated regarding awareness of insulin infusion failure (rising blood glucose levels and ketones) and how to manage this (using standard injected subcutaneous insulin, and change insulin infusion set).
- f. At each clinic visit, data will be forwarded to the principal investigator. Any admissions to hospital for DKA or severe hypoglycaemia will reported to the principal investigator with 24hrs.
- g. Establishment of Data and Safety Monitoring Board (DSMB) to review progress

All serious adverse events are to be recorded and reported to the investigators within 24 hours of notification to lead site and sponsor as well as other regulatory bodies i.e. TGA. All Severe Adverse Events, whether related to the investigational device or not will be reported to the device manufacturer.

